9.6 ADVERSE EVENTS OF SPECIAL INTEREST (AESI)

Subjects will be assessed for diagnosis of an AESI at all study visits. AESIs include PIMMCs, AEs specific to COVID-19, or other potential AEs that may be determined at any time by regulatory authorities as additional information concerning COVID-19 is obtained. Listings of AESI are presented in Appendix I.

9.7 SEVERITY OF ADVERSE EVENTS

The grading scales cited below will be used to interpret the severity of each AE as such:

Grade 1 = Mild

Grade 2 = Moderate

Grade 3 = Severe (a severe AE is not necessarily an SAE, unless it meets one of the criteria that define an SAE; likewise, all SAEs are not necessarily by definition severe)

Grade 4 = Potentially Life-threatening (life-threatening AEs are to be reported as SAEs)

Grade 5 = Death

The severity of all AEs, listed specifically as an event in the Division of AIDS (DAIDS) Table for Grading the Severity of Adult and Pediatric Adverse Events, corrected version 2.1, July 2017, of the US National Institute of Health, will be assessed based on this Table, which is provided as Appendix III to this protocol and is currently also available at: https://rsc.niaid.nih.gov/sites/default/files/daidsgradingcorrectedv21.pdf

CONFIDENTIAL Page 55 of 94

The following grading scale should be used to grade the severity of all unsolicited AEs that are not listed as a specific event in the DAIDS Table cited:

- Grade 1= Causes no or minimal interference with usual social & functional activities
- Grade 2 = Causes greater than minimal interference with usual social & functional activities
- Grade 3 = Causes inability to perform usual social & functional activities
- Grade 4 = Potentially life-threatening symptoms causing inability to perform basic self-care functions with intervention indicated to prevent permanent impairment, persistent disability Grade 5 = Death

9.8 CAUSALITY OF ADVERSE EVENTS

The investigator will determine the causal relationship between the vaccine and the AE for all unsolicited AEs. The causality assessment is made based on the available information at the time of reporting and can subsequently be changed according to follow-up information. Causality determination is based on clinical assessment and should take into consideration the following factors:

- Is there a temporal relationship between the event and administration of the vaccine?
- Is there a plausible biological mechanism for the vaccine to cause the AE?
- Is there a possible alternative etiology for the AE, such as a concurrent illness or a concomitant medication?
- Are there previous reports of similar AEs associated with the vaccine or other vaccines in the same class?

For this study, the investigator must classify the causality of the AE according to the categories defined below:

Related: There is a reasonable possibility that the vaccine caused the event. 'Reasonable possibility' means that there is evidence to suggest a causal relationship between the vaccine and the AE.

Not Related: There is not a reasonable possibility that the administration of the vaccine caused the event.

All solicited AEs within 7 days of each vaccination will be considered as related AEs unless there is reasonable possibility of any systemic solicited AE being caused by any other concurrent condition / disease. In addition, related SAEs will be evaluated by the investigator for "expectedness" also. An unexpected AE is one that is not listed in the current Summary of

CONFIDENTIAL Page 56 of 94

Product Characteristics / prescribing information or the IB or it is an event that is by nature

Version: 4.0 Dated 21 Apr 2022

more specific or more severe than a listed event.

9.9 FOLLOW-UP OF ADVERSE EVENTS

All AEs should be followed by the investigator or their designee until the event is resolved or

determined to be irreversible, chronic, or stable by the investigator or participant is lost to

follow up (including death). The investigator must ensure that any participants with AEs

ongoing at study completion are advised or referred appropriately for continuation of care.

The outcome of an AE will be assessed as at the time of last observation per the following

categories:

Recovered without sequelae

Recovered with sequelae

Ongoing

Death

Unknown

9.10 GENERAL GUIDANCE ON REPORTING ADVERSE EVENTS

To improve the quality and precision of AE data, the investigator should observe the following

guidelines:

• AEs must be graded, assessed for severity and causality, and reviewed by a site

investigator.

Whenever possible, use recognized medical terms when reporting AEs and avoid the use

of colloquialisms or abbreviations.

If known, report the diagnosis (i.e., syndrome or disease) rather than component

symptoms, signs or laboratory values (e.g., report congestive heart failure rather than

dyspnoea, rales, and cyanosis); however, symptoms or signs that are considered unrelated

to an observed syndrome or disease should be reported as individual AEs (e.g., if

congestive heart failure and severe headache are observed at the same time, each event

should be recorded as an individual AE).

• AEs occurring secondary to other events (e.g., sequelae) should be identified by the

primary cause. A 'primary' AE, if clearly identifiable, generally represents the most

accurate clinical term to report. For example: orthostatic hypotension \rightarrow fainting and fall

CONFIDENTIAL Page 57 of 94

to floor \rightarrow head trauma \rightarrow neck pain; the primary AE is orthostatic hypotension, which is what should be reported. If a primary SAE is reported, events occurring secondary to the primary event should be described in the narrative description of the case.

- Death is an outcome of an event. The event that resulted in the death should be reported as the SAE.
- For hospitalizations for surgical or diagnostic procedures, the illness leading to the surgical or diagnostic procedure should be recorded as the SAE, not the procedure itself.
 The procedure should be captured in the case narrative as part of the action taken in response to the illness.
- Elective surgical or diagnostic procedures with or without hospitalizations (e.g., circumcision or elective abortion of a pregnancy) will not be recorded as an AE. The procedure should be captured in the case narrative as part of medical history.
- A pregnancy in a participant is not in and of itself an AE.

9.11 REPORTING OF SAE

Any SAE occurring in a study participant during the study (after vaccine administration) must be reported. Information about all SAEs will be collected and recorded in SAE form. To ensure participant safety, each SAE must be reported by the Investigator to the Sponsor within 24 hours of learning of its occurrence, even if it is not felt to be treatment-related.

The SAE form will always be completed as thoroughly as possible with all available details of the event. Even if the investigator does not have the entire recommended minimum information regarding a SAE, the SAE should still be submitted to sponsor, DCGI and respective IEC within 24 hours. Once additional relevant information is received, the SAE form should be updated. Reporting procedures will be followed as per the New Drugs and Clinical Trials Rules, 2019.

The investigator will always provide an assessment of causality at the time of the initial report.

Instructions for reporting of SAEs

The recommended minimum information required for the initial SAE report is:

- Identifiable study participant
- A suspect medicinal product
- Identifiable reporting source

CONFIDENTIAL Page 58 of 94

- An event or outcome that can be identified as SAE
- Preliminary causality assessment
- Severity

All SAEs are also to be documented on the Adverse Events eCRF. Any medication or other therapeutic measures used to treat the AE will be recorded on the appropriate eCRF pages in addition to the grading and outcome of the AE.

Version: 4.0 Dated 21 Apr 2022

Contact Persons and Numbers

The details of the Sponsor's contact person for safety reporting or questions are listed below and will also be kept on-site in the Investigator File.

Follow-up of SAEs

After receipt of the initial report, sponsor/designee may contact the investigator if it is necessary to obtain further information for assessment of the event.

CONFIDENTIAL Page 59 of 94

All SAEs must be documented and followed up until the event has resolved, subsided,

Version: 4.0 Dated 21 Apr 2022

on one or more consecutive SAE report forms in a timely manner.

9.12 TREATMENT OF AE AND SAES

Treatment of any AE and SAE is at the sole discretion of the investigator and according to current Good Medical Practice. The applied measures should be recorded in eCRF.

stabilized, or is otherwise explained. All follow-up activities have to be reported, if necessary

Cost of the medical care for vaccine related AEs will be borne by the sponsor.

10. STATISTICAL CONSIDERATIONS

10.1 OVERVIEW AND GENERAL CONSIDERATIONS

This is a Phase 3, observer-blind, randomised, active controlled study in adults aged ≥ 18 years in India who have already received primary vaccination against COVID-19 at least 6 months ago (6 months / 180 days from the second dose), to evaluate the immunogenicity and safety of the COVOVAX booster dose in comparison with the control vaccine (COVISHIELD and COVAXIN, for COVISHIELD and COVAXIN Prime cohorts, respectively).

A detailed statistical analysis plan will be created and finalized prior to database lock. All statistical analyses will be performed using SAS® software Version 9.4 or later. Additional details for statistical analysis will be included in the SAP.

Medical History and AEs will be coded using the Medical Dictionary for Regulatory Activities (MedDRA) (version 23.0 or later). The frequency count and percentage of participants will be summarized by system organ class (SOC) and preferred term (PT). Study participant-wise data listing will be provided.

Non-inferiority of COVOVAX booster over an active control vaccine group for each cohort will be concluded if both the lower limit of the two-sided 95% CI for the GMT ratio (GMR) >0.67 and the lower limit of the two-sided 95% CI for the difference in proportions of participants with ≥2-fold rise is >-10% for both anti-S IgG and nAbs between COVOVAX and the Control vaccine groups at Day 29. For consistency two-sided 95% confidence intervals (CIs) will be provided throughout. The main purpose of the safety analysis is to estimate the incidence rate of different events in each vaccine group.

No statistical tests will be performed at any interim analyses of safety data.

CONFIDENTIAL Page **60** of **94**

10.2 RANDOMIZATION

The randomization scheme for treatment assignment (vaccine groups) will be generated and maintained by independent personnel at PPD. PPD Biostatistics will generate the randomization schedule using SAS software Version 9.4 or later (SAS Institute Inc, Cary, North Carolina) for Interactive Response Technology (IRT), which will link sequential participant randomization numbers to treatment codes.

Version: 4.0 Dated 21 Apr 2022

The eligible participants will be enrolled and randomized in the study online through IRT. Each participant enrolled into the study will be assigned a randomization number to assign vaccine group after identification and eligibility data have been entered into the IRT system.

A total of 372 eligible participants of \geq 18 years of age who have completed primary 2 dose schedule of COVID-19 vaccination at least 6 months ago will be enrolled in the study in 2 cohorts of 186 participants each with 1:1 allocation to COVOVAX or control vaccine. All eligible participants (n=372) will receive 0.5 ml of either COVOVAX or the Control vaccine (COVISHIELD or COVAXIN in the respective cohort) on Day 1 as per randomization.

10.3 MULTIPLICITY

This trial has two separate cohorts with their own type I error family. There are four coprimary endpoints in each study cohort: GMR and difference in proportions of participants with at least 2-fold increase measured in anti-S IgG and nAb between COVOVAX and the active control vaccine at Day 29 after booster vaccination. To claim success of the primary objective in a cohort, all four null hypotheses of non-inferiority are required to be rejected at one-sided alpha level of 0.025 for each of them. No additional multiplicity adjustment will be performed.

10.4 SAMPLE SIZE AND POWER

It is planned to randomize 372 participants in the study with 186 in each of 2 cohorts who have received primary vaccination with either COVISHIELD OR COVAXIN. Assuming that the proportion of non-evaluable participants ≤ 15% (which leads to a sample size of 158 evaluable participants for each cohort), group sample sizes of 93 each in the tested vaccine group and the active control group achieve 80% power to detect non-inferiority using a one-sided, two-sample t-test. The margin of non-inferiority is -0.33. The true ratio of the means at which the power is evaluated is 1.00. The one-sided significance level (alpha) of the test is 0.025. The

CONFIDENTIAL Page 61 of 94

coefficients of variation of both groups are assumed to be 1.1. Non-inferiority of COVOVAX booster over an active control vaccine group for each cohort will be concluded separately if the lower limit of the two-sided 95% CI for the GMT ratio for both anti-S IgG antibodies and neutralizing antibodies between COVOVAX and the active control vaccine at Day 29 is > 0.67 (non-inferiority margin).

With the same sample size and randomization ratio, the study will achieve 82% power to detect non-inferiority using a one-sided, two-sample z-test for difference in two proportions of participants achieving \geq 2-fold increase. The margin of non-inferiority is -10%. The true difference of the proportion at which the power is evaluated is 0 and the proportion in the active control group is assumed 95%. The one-sided significance level (alpha) of the test is 0.025.

Sample size calculations were performed using a non-inferiority test for the ratio of two means and difference in two proportions in PASS 15.0.7 Version software.

The following table shows the evaluable sample size to demonstrate noninferiority of immune response:

	Power Evaluable sample size		ze (SS)	% Non-		
Cohort	GMR	Diff. of Prop. of participants with ≥2-fold rise	Total number of participants	COVOVAX	Control (Covishield/ Covaxin for respective cohort)	evaluable participants (Dropout rate)
COVISHIELD	80	82	158	79	79	15%
Prime cohort						
COVAXIN	80	82	158	79	79	15%
Prime cohort						

Based on sample size of each arm, the 95% confidence interval for safety events are:

True safety		(95% Exact binomial Cl	[
event rate	COVOVAX (N=93)	Active Control (N=93)	One Cohort (either COVISHIELD Prime or COVAXIN Prime) (N=186)	COVOVAX Booster Combined (N=186)	Overall (N=372)
1.0%	0% -5.7%	0% -5.7%	0.1% - 3.7%	0.1% - 3.7%	0.3% - 2.6%
2.0%	0.2% - 7.3%	0.2% - 7.3%	0.5% - 5.2%	0.5% - 5.2%	0.8% - 4.0%
5.0%	1.6% – 11.6%	1.6% - 11.6%	2.3% - 9.2%	2.3% - 9.2%	3.0% - 7.7%
10.0%	4.7% - 18.0%	4.7% - 18.0%	6.1% - 15.2%	6.1% - 15.2%	7.1% - 13.5%

CONFIDENTIAL Page 62 of 94

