It is planned to randomize 372 participants with 186 in each of 2 cohorts who have received primary vaccination with either COVISHIELD OR COVAXIN. Assuming that the proportion of non-evaluable participants \leq 15% (which leads to a sample size of 158 evaluable participants for each cohort), group sample sizes of 93 each in the tested vaccine group and the active control group achieve at least 80% power to detect non-inferiority using a one-sided, two-sample t-test. The margin of non-inferiority is -0.33. The true ratio of the means at which the power is evaluated is 1.00. The onesided significance level (alpha) of the test is 0.025. The coefficients of variation of both groups are assumed to be 1.1. Non-inferiority of COVOVAX booster over an active control vaccine group for each cohort will be concluded separately if the lower limit of the two-sided 95% CI for the GMT ratio for both anti-S IgG and neutralizing antibodies between COVOVAX and the active control vaccine at Day 29 is > 0.67. The same sample size to serve the statistical test for a non-inferiority difference in proportion of participants achieving ≥ 2-fold increase in Anti-S and nAbs between COVOVAX and the active control vaccine at Day 29 will achieve 82% power, using a one-sided, two-sample z-test at alpha level of 0.025. Proportion of participants achieving \geq 2-fold increase in both Anti-S and nAbs for COVISHILED/ COVAXIN arm is assumed 95% and the margin of non-inferiority is -10%. The true difference of the proportion at which the power is evaluated is 0. Sample size calculations were performed using a non-inferiority test for the ratio of two means and difference in two proportions in PASS 15.0.7 Version software.

To assess the co-primary objectives, the non-inferiority hypotheses will be tested on the GMR between COVOVAX and COVISHIELD or COVOVAX

Confidential Page 15 of 94

and COVAXIN for anti-S IgG and nAbs at 28 days (Day 29) post study vaccination using an ANCOVA model for each cohort. The lower limit of the 95% CI will be compared with the non-inferiority margin 0.67 and COVOVAX will be declared non-inferior to the active Control vaccine, COVISHIELD or COVAXIN in each cohort if it is greater than 0.67.

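### The 80% and 82% in section 10.4 are powers for one endpoint in one assay; power for the four-of-four rule that decides each cohort is not given and is well below 80% at the plan's own assumptions

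*Protocol*

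**What the plan says.** **Success rule.** Section 10.3 names four co-primary endpoints per cohort and states: "To claim success of the primary objective in a cohort, all four null hypotheses of non-inferiority are required to be rejected". Each is tested at one-sided 0.025, with no further adjustment. Section 10.1 gives the same rule in terms of confidence limits: GMR limit above 0.67 and difference limit above -10%, for both assays.

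**Power statement.** Section 10.4 says that "group sample sizes of 93 each in the tested vaccine group and the active control group achieve 80% power to detect non-inferiority", by a one-sided two-sample t-test. The Protocol Summary (Statistical considerations) puts it more strongly: "achieve at least 80% power to detect non-inferiority using a one-sided, two-sample t-test". For the responder endpoint, section 10.4 says "the study will achieve 82% power to detect non-inferiority using a one-sided, two-sample z-test for difference in two proportions". The table in 10.4 repeats 80 and 82 in separate columns for the GMR and the difference in proportions, against 79 evaluable per arm and 15% non-evaluable.

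**How the two are linked.** In both places the 80% is followed by a criterion that requires the GMR limit to hold for both anti-S IgG and neutralizing antibodies. The Protocol Summary attaches the 82% to the 2-fold rise in both assays. Nowhere is a power given for two assays together or for all four tests, and no correlation between endpoints is assumed.

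**The concern.** An all-must-pass rule needs no alpha adjustment, but it costs power: every added test is another chance to miss. The sample size is justified by the power of one test, while the cohort conclusion needs four. A reader who takes 80% as the chance of concluding non-inferiority in a cohort, with truly equal vaccines, would put the risk of failure near 20%. At the plan's own assumptions it is considerably higher. The sponsor, ethics committees and regulator rely on this figure, and a missed criterion could be misread as evidence of inferiority when the design was simply not sized for the joint rule.

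**Working it through.** **Inputs, all from section 10.4 unless noted.** One-sided alpha 0.025; GMR margin 0.67 (written as -0.33); true ratio 1.00; CV 1.1 in both groups; responder proportion 95% in control, true difference 0, margin -10%; 79 evaluable per arm (186 × 0.85 = 158.1 per cohort). Four-of-four rule from section 10.3.

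**1. Reproduce the 80% (one GMR, one assay).**
- Log-scale SD = √ln(1 + 1.1²) = 0.8905.
- Distance to the margin = -ln(0.67) = 0.4005.
- Standard error = 0.8905 × √(2/79) = 0.1417.
- Noncentrality = 0.4005 / 0.1417 = 2.826.
- Power of a t-test with 156 degrees of freedom = **80.2%**.

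**2. Reproduce the 82% (one responder difference, one assay).**
- Standard error = √(2 × 0.95 × 0.05 / 79) = 0.0347.
- 0.10 / 0.0347 = 2.884, and Φ(2.884 - 1.960) = **82.2%**.

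Both figures are therefore right as single-test powers at 79 per arm. At the 93 per arm named in the sentence they would be 86% and 88%, so the 93 is the randomised number and the power belongs to the 79.

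**3. Two GMRs only (both assays).** 0.80² = 64% if independent, 69% at an assumed test-statistic correlation of 0.5, and 75% at 0.9. The 80% does not hold even for the two-assay GMR criterion that follows it in the text.

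**4. All four tests.** Independence: 0.80² × 0.82² = 0.640 × 0.672 = **43.0%**. With correlation, the joint power is P(Z₁ < z₀.₈₀, Z₂ < z₀.₈₀, Z₃ < z₀.₈₂, Z₄ < z₀.₈₂) for a four-variate normal with a common correlation. The protocol gives no correlation, so these values are assumptions:

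| Assumed common correlation of test statistics | Four-of-four power |
|---|---|
| 0 | 43% |
| 0.3 | 51% |
| 0.5 | 57% |
| 0.7 | 63% |
| 0.9 | 71% |

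The probability of passing all four tests cannot exceed that of passing the weakest one, so 80% is the ceiling from the stated figures. It is reached only under near-perfect dependence.

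**5. Two influences outside the stated calculation.**
- *Downward:* the planned Miettinen-Nurminen interval has an exactly enumerated power of about 70% per responder endpoint at 79 per arm, against 82% for the z-test. Joint power under independence would then be 0.80² × 0.7036² = 32%. This is a separate mismatch between sizing method and analysis method.
- *Upward:* section 10.6.3 plans an ANCOVA with log baseline titer and other covariates. If these explained 30% of the Day 29 variance (an assumption), GMR power would be about 92%. Joint power with the stated 82% would be 0.922² × 0.82² = 57% under independence, and a little over 71% at correlation 0.7.

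**The case against.** **Nothing is miscalculated, and the table separates GMR from proportions.** Both true. The defect is one of labelling and of a missing figure. The columns separate the two endpoint types but not the two assays, and none refers to the rule in section 10.3.

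**The protocol never calls 80% the power for all four tests.** Also true. A reader might infer that the sponsor claims 80% for cohort success; the documents do not say so. They place the single-test figure directly beside a conclusion that needs both assays, and give nothing for the rule that decides.

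**Equality is a cautious planning point.** This stands as a limit on interpretation. If, for illustration, the true GMR were 1.2 and responders 97% against 95%, the single-test powers would be about 98.4% and 97.1%. Joint power under independence would be 0.984² × 0.971² = 91%. But section 10.4 evaluates power at ratio 1.00 and difference 0, and the stated figures should be read at those values.

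**A stronger reading to resist.** One might conclude that each cohort has only a 35% to 50% chance of success and that the 80% sentence should be deleted. The low end of that range brings in the separate Miettinen-Nurminen issue. The high end is too low once correlation or covariate adjustment is allowed. The 80% itself is correct for one GMR in one assay.

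**Type I error is not affected.** Agreed: requiring all four rejections at 0.025 is valid without adjustment, and a positive result would stand.

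**Conclusion.** The point holds as a mismatch between the power statement and the decision rule. At the planning values, and from the stated 80% and 82%, four-of-four power per cohort is 43% if the tests are independent and about 51% to 63% at assumed test-statistic correlations of 0.3 to 0.7. It cannot exceed 80%. The exact value cannot be fixed from the protocol, because it depends on correlations that the protocol does not give, on the interval method for proportions, and on how much variance the ANCOVA covariates explain. The conclusion that the design lacks 80% power for its own success rule does not depend on choosing among the tabulated correlations. Nothing here shows that the sample size is invalid or that a positive finding would be unsound.

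**What to change.** In section 10.4, its table and the Protocol Summary:

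1. Keep the 80% and 82%, but label each as the power for one endpoint in one assay with 79 evaluable participants per arm (93 randomised).
2. In the Protocol Summary, drop *at least* as a claim about the cohort conclusion, so that 80% is not read as covering both assays.
3. Add the power per cohort for rejecting all four nulls at ratio 1.00 and difference 0. State the assumed correlations, the method used for the proportions, and whether covariate adjustment is credited. On the present calculation the entries would be 43% at correlation 0 and about 51%, 57% and 63% at 0.3, 0.5 and 0.7.

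The cost is a few words and one table column, and a less favourable stated figure. No change in enrolment is required. If the sponsor did want about 80% joint power, the z-test basis would need roughly 126 evaluable per arm under independence, or 2 × ⌈126/0.85⌉ = 298 randomised per cohort, and fewer with positive correlation. That is a design choice, not part of this correction.

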10.6.3 Table of Statistical Method and Sensitivity Analysis

		Main Estimation			Sensitivity	
Estimand Label	Estimand Description	Analysis Set	Imputation/ Data/ Censoring Rules	Analysis Model/Method	Analysis	
Estimand 1.1a, Estimand 1.2a (Co-Primary)	Geometric Mean ratio (GMR) of anti-S IgG at 28 days after vaccination between vaccines (COVOVAX booster/ control) for each cohort Principal Stratum is used to understand antibody levels achieved through vaccination, without subsequent COVID-19/SARS-CoV-2 infection or use of any immune-modifying medications or other vaccines. While on treatment strategy is used for event death.	Per protocol Population	Values below the limit of quantification (LOQ) or limit of detection (LOD) will be replaced by LOQ/2 and LOD/2, respectively before log transformation. Multiple imputation of missing values assumed to MAR.	ANCOVA will be fitted to the log transformed anti-S IgG or nAbs with terms for vaccine group, log baseline titer, age, sex, duration between 1st - 2nd vaccine dose, duration between 2nd dose to booster dose of vaccine. Individual mean and 95% CI values by treatment from this model will be used to generate the geometric mean titers (GMT) at each time point and geometric mean ratio (GMR) with 95% CI at Day 29 after vaccination by back transforming to the original scale. This analysis will be performed for each type antibody (anti-S IgG or nAbs) and cohort separately. Hypothesis testing: H₀: GMTT/GMTC ≤ 0.67 H₁: GMTT/GMTC > 0.67 Where, T = COVOVAX and C=Active Control vaccine (COVISHIELD or COVAXIN). The lower limit of the 95% CI for the GMR will be compared with a noninferiority margin of 0.67 and COVOVAX vaccine will be declared noninferior to the Control vaccine (COVISHIELD or COVAXIN) if > 0.67 on both anti-S IgG antibody and nAbs.	Supplementary: Similar repeat analysis based on Full Analysis population will be provided. Hypothetical is used to understand antibody levels achieved through vaccination, without subsequent COVID- 19/SARS-CoV- 2 infection or use of any immune- modifying medications or other vaccines.	

Confidential Page 74 of 94

Study Protocol: COVOVAX-Booster Version: 4.0 Dated 21 Apr 2022

		Main Estimation			Sensitivity
Estimand Label	Estimand Description	Analysis Set	Imputation/ Data/ Censoring Rules	Analysis Model/Method	Analysis

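### The synopsis and section 10.4 conclude cohort-level non-inferiority on the two GMRs alone, while sections 10.1 and 10.3 also require both fold-rise criteria

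*Protocol*

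**What the plan says.** Two sections condition the cohort-level conclusion on four tests.

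- Section 10.1 sets a two-part condition, under which the claim is "concluded if both the lower limit of the two-sided 95% CI for the GMT ratio (GMR) >0.67 and the lower limit"; the sentence then names fold-rise, whose interval must lie above -10% in each assay.
- Section 10.3: "To claim success of the primary objective in a cohort, all four null hypotheses of non-inferiority are required to be rejected", each at one-sided 0.025, with no further adjustment.

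Two places condition it on the GMRs alone.

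- Section 10.4: the claim in a cohort is "concluded separately if the lower limit of the two-sided 95% CI for the GMT ratio for both anti-S IgG antibodies and neutralizing antibodies", with 0.67 as the bound.
- Protocol Summary, Statistical considerations: the same rule, "concluded separately if the lower limit of the two-sided 95% CI for the GMT ratio for both anti-S IgG and neutralizing antibodies".

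The Summary lists all four endpoints as co-primary and later gives a separate declaration for fold-rise, but it never says that all four must pass.

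The method table in 10.6.3 has one row for the GMR estimands (1.1a, 1.2a), where COVOVAX is "declared noninferior to the Control vaccine (COVISHIELD or COVAXIN) if > 0.67 on both anti-S IgG antibody and nAbs". The row for the fold-rise estimands (1.1b, 1.2b) has a parallel declaration against -10%. Section 10.6.5 repeats the pair as items 1 and 2.

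**The concern.** The sentences in 10.1 and 10.4 open almost identically and reach the same conclusion, non-inferiority of the booster in a cohort, under different conditions. Section 10.4 does not say that the GMR criterion is met; it says that non-inferiority is concluded. Nothing ranks 10.3 above 10.4, and someone working from the Summary alone would apply the GMR-only rule.

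What is at stake is the primary verdict in each of the two cohorts. If both GMR lower limits clear 0.67 and a fold-rise lower limit does not clear -10%, one part of the protocol supports the claim and another forbids it. A claim resting on the GMRs alone would leave the two fold-rise hypotheses, which the protocol also calls co-primary, without support.

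**Working it through.** **1. The two rules side by side**

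| Result in a cohort | Summary and 10.4 | 10.1 and 10.3 |
|---|---|---|
| All four pass | claim | claim |
| Both GMRs pass, at least one fold-rise fails | claim | no claim |
| At least one GMR fails | no claim | no claim |

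The rules are nested, so only the middle row differs. Its probability is P(both GMRs pass) minus P(all four pass).

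**2. Inputs (section 10.4)**

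One-sided alpha 0.025; GMR margin 0.67 (written as -0.33); true ratio 1.00; CV 1.1; fold-rise 95% in the control arm with true difference 0; fold-rise margin -10%; 158 evaluable per cohort, 79 per arm. Stated power is 80% for the GMR and 82% for fold-rise. The correlation between the assays, and between titre and fold-rise, is not given.

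**3. Reproducing the stated powers**

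- GMR: log-scale SD = sqrt(ln(1 + 1.1²)) = 0.8905. SE = 0.8905 × sqrt(2/79) = 0.1417. Margin = -ln(0.67) = 0.4005. 0.4005/0.1417 - 1.96 = 0.87, so power is 80.7% (normal) or 80.2% (t). The stated 80% reproduces.
- Fold-rise, unpooled z: SE = sqrt(2 × 0.95 × 0.05/79) = 0.0347. 0.10/0.0347 - 1.96 = 0.92, so power is 82.2%. The stated 82% reproduces.
- Evaluable number: 186 × 0.85 = 158.1, which reproduces 158.

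**4. Disagreement from the stated powers**

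Under independence:

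- Both GMRs pass: 0.80² = 0.640.
- All four pass: 0.640 × 0.82² = 0.640 × 0.6724 = 0.430.
- Difference: 0.210, or 21% of cohorts.

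Simple correlation patterns move this figure:

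- Fold-rise tests perfectly correlated, GMRs independent: 0.64 × 0.18 = 11.5%.
- The two assays perfectly correlated: 0.80 × 0.18 = 14.4%.
- GMRs perfectly correlated, fold-rise tests independent: 0.80 × 0.3276 = 26.2%.

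The range is about 12% to 26%.

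**5. Disagreement with the planned interval**

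The fold-rise power was computed with a z-test, but the planned interval is Miettinen-Nurminen (Summary and 10.6.3). Exact enumeration at 79 per arm and 95% in both arms gives 70.4% power with that interval. With GMR power 80.2% and independence: 0.802² = 0.643; 0.643 × 0.704² = 0.318; difference 32%.

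Simulation used 20,000 trials per setting, a t-test for the GMR, Miettinen-Nurminen for fold-rise and 79 per arm. Selected settings:

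| Correlation between assays | Correlation titre/fold-rise | Both GMRs pass | All four pass | Difference |
|---|---|---|---|---|
| 0 | 0 | 64.2% | 31.8% | 32.4% |
| 0.5 | 0.5 | 68.3% | 39.0% | 29.3% |
| 0.8 | 0.5 | 72.9% | 43.6% | 29.3% |
| 0.95 | 0.8 | 76.0% | 50.9% | 25.1% |

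Over all settings run (0 to 0.95 between assays, 0 to 0.8 between titre and fold-rise) the difference is 25% to 33%. With the z-test instead it is 16% to 22%. With all 93 per arm evaluable and the planned interval it is 21% to 28%.

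**The case against.** The strongest reply is that the protocol does fix the rule. Section 10.3 is the multiplicity section, it states the success criterion in so many words, and 10.1 agrees. The sentence in 10.4 closes the paragraph on GMR power; the fold-rise power follows at once, and the table lists both. This stands in part: 10.3 is the clearest statement, and it points to the intended rule. It does not remove the contradiction, because 10.4 and the Summary state a conclusion about the booster in a cohort and not about one criterion.

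Three stronger readings are tempting, and the documents do not support them.

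- A reader might take 10.6.3 and 10.6.5 as further GMR-only cohort rules. They are not: the GMR and fold-rise entries are parallel, so they read as endpoint-level declarations. Taken literally, they would also create a fold-rise-alone rule, which nobody intends.
- A reader might infer that doing without multiplicity adjustment is valid only under the four-of-four rule. The both-GMR rule is also an all-must-pass test at 0.025 each. Because the rules are nested, a free choice between them is simply the GMR-only rule and adds no type I error to the GMR claim. What changes is the content of the claim.
- A reader might infer that the decision rule is open and could be picked after the data are seen. The explicit pre-specification in 10.3 speaks against that.

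**Conclusion.** The contradiction holds as written: the Summary and 10.4 against 10.1 and 10.3. It affects the primary conclusion in each cohort, always in the same direction, with the GMR-only wording the more permissive.

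The protocol states no rate of disagreement, so any size is derived. It is about 21% of cohorts from the stated powers under independence, and about 25% to 33% with the planned Miettinen-Nurminen interval at 79 per arm. All of these figures assume identical vaccines, a 95% fold-rise rate in both arms and correlations that the protocol does not give. A single figure of about 30% should not be presented as following from the plan's stated powers. Nor should the conditional figure be read as a share of all cohorts: given that both GMRs pass, the chance that a fold-rise test fails is 1 - 0.82² = 33% from the stated powers under independence.

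**What to change.** Make the four-of-four rule in 10.3 the only cohort-level success rule.

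- In the Protocol Summary and 10.4, replace the GMR-only conclusion with the 10.1 rule, or say only that the GMR co-primary criterion is met.
- State the four-of-four rule once in the Summary, where it is absent.
- For consistency, word the separate GMR and fold-rise declarations in the Summary, both co-primary rows of 10.6.3 and both items of 10.6.5 as endpoint-level criteria, and refer to 10.3 for the cohort claim.

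The cost is wording in an amendment. Sample size, data collection and analyses do not change.
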